Description of Interventions:	
a) The Na-APR-1 (M74) candidate vaccine contains recombinant Na-APR-1 (M74) adsorbed onto aluminum hydroxide gel (Alhydrogel®) and suspended in a solution containing 10mM imidazole, 150mM sodium chloride and 0.3% Empigen BB, with pH 7.4 ± 0.1. The final concentrations of Na-APR-1 (M74) and Alhydrogel® in the drug product are 0.1mg/ml and 0.8mg/ml, respectively. Doses of 10, 30 and 100 µg Na-APR-1 (M74) will be delivered IM to the deltoid by injecting different volumes of the 0.1mg/ml preparation.b) The Na-GST-1 candidate vaccine contains the recombinant Na-GST-1 adsorbed onto Alhydrogel® and suspended in a solution containing 10mM imidazole and 10% glucose. The final concentrations of Na-GST-1 and Alhydrogel® in the drug product are 0.1mg/ml and 0.8mg/ml, respectively. Only one dose of Na-GST-1 will be tested (100µg), at a volume of 1.0ml delivered IM to the deltoid.c) Gluco-Pyranosylphospho-Lipid A Aqueous Formulation (GLA-AF) is a Toll-like Receptor-4 agonist. Point-of-injection formulations with this immunostimulant will be prepared immediately prior to vaccination by adding an appropriate volume of GLA-AF to Na-APR-1 (M74) and withdrawing an appropriate volume to administer the desired amount of Na-APR-1 (M74) plus 5µg GLA-AF IM to the deltoid.d) The ENGERIX-B hepatitis B vaccine will serve as the comparator vaccine. Each 0.5 ml dose contains 20 µg recombinant hepatitis B surface protein expressed by

Saccharomyces cerevisiae and adsorbed to aluminum hydroxide will be injected IM to the deltoid.

- e) To maintain the study blind by ensuring that all subjects receive two injections at each vaccination point, sterile normal saline (0.9%) for injection will be co-administered to those subjects randomized to receive Hepatitis B vaccine.

Objectives:

Primary:

Safety

1. To evaluate the safety and reactogenicity of three different dose concentrations of *Na-APR-1* (M74)/Alhydrogel® co-administered with *Na-GST-1*/Alhydrogel® in healthy Gabonese children.

Secondary:

Immunogenicity

1. To determine the doses of co-administered *Na-APR-1* (M74) and *Na-GST-1* that result in the highest levels of IgG antibody approximately 14 days after the third vaccination.

Tertiary:

Immunogenicity

1. To assess and compare the duration of the antibody responses of *Na-GST-1* and *Na-APR-1* (M74).
2. To assess the distribution of IgG subclass responses to *Na-GST-1* and *Na-APR-1* (M74).

Exploratory:

1. To assess the cellular immune responses to the *Na-GST-1* and *Na-APR-1* (M74) antigens following immunization.
2. To assess the impact of co-administered *Na-GST-1* and *Na-APR-1* (M74) on the production of memory B cells specific for each antigen.
3. To assess the production of memory B cells specific for each vaccine antigen compared to metabolomic changes before and after vaccination
4. To characterize the metabolite composition in urine and serum during the course of immunization and assess the changes on metabolite profiles related to the co-administration of *Na-GST-1* and *Na-APR-1* (M74).

Description of Study Design:

Double blind, randomized, controlled, dose-escalation Phase 1 clinical trial in hookworm-exposed children aged 6 to 10 years living in the area of Lambaréne, Gabon. Children will receive three doses of the assigned vaccine(s) delivered intramuscularly (deltoid) on approximately Days 0, 56, and 112 or 180.

Safety will be measured from the time of each study vaccination (Day 0) through 14 days after each study vaccination by the occurrence of solicited injection site and systemic reactogenicity events.

Unsolicited non-serious adverse events (AEs) will be collected from the time of the first study vaccination through approximately 1 month after each study vaccination. New-onset chronic medical conditions and Serious Adverse Events (SAEs) will be collected from the time of the first study vaccination through approximately 9 months after the third study vaccination (final visit). Clinical laboratory evaluations for safety will be performed on venous blood collected approximately 14 days after each vaccination.

Immunogenicity testing will include IgG antibody responses to each vaccine antigen, by a qualified indirect enzyme-linked immunosorbent assay (ELISA), on serum or plasma obtained prior to each study vaccination and at time points after each vaccination (see Appendix A); the functional activity of vaccine-induced antibodies will be assessed by *in vitro* enzyme neutralization assays; the induction of B cell memory will be measured by antigen-specific memory B cell responses.

Recruitment and enrollment into the study will occur on an ongoing basis, with each group being recruited and vaccinated in sequence.

60 subjects will be enrolled into 3 groups of 20:

The first 20 subjects will be assembled and enrolled into Group 1:

- Group 1 double-blind IP allocation (n=20):
 - 16 subjects will receive 10 µg *Na-APR-1* (M74) plus 5 µg GLA-AF delivered by IM injection in the deltoid muscle, with 10 µg *Na-GST-1* administered IM in the alternate arm.
 - 8 will be vaccinated according to a 0,2,4-month schedule
 - 8 will be vaccinated according to a 0,2,6-month schedule

[figure not shown]
- 4 subjects will receive hepatitis B vaccine comparator:
 - 2 will be vaccinated according to a 0,2,**4**-month schedule
 - 2 will be vaccinated according to a 0,2,**6**-month schedule
- Group 2 double-blind IP allocation (n=20):
 - 16 subjects will receive 30 µg *Na-APR-1* (M74) plus 5 µg GLA-AF delivered by IM injection in the deltoid muscle, with 30µg *Na-GST-1* administered IM in the alternate arm.
 - 8 will be vaccinated according to a 0,2,**4**-month schedule
 - 8 will be vaccinated according to a 0,2,**6**-month schedule
 - 4 subjects will receive hepatitis B vaccine comparator:
 - 2 will be vaccinated according to a 0,2,**4**-month schedule
 - 2 will be vaccinated according to a 0,2,**6**-month schedule
- Group 3 double-blind IP allocation (n=20):
 - 16 subjects will receive 100 µg *Na-APR-1* (M74) plus 5 µg GLA-AF delivered by IM injection in the deltoid muscle, with 100 µg *Na-GST-1* administered IM in the alternate arm.
 - 8 will be vaccinated according to a 0,2,**4**-month schedule
 - 8 will be vaccinated according to a 0,2,**6**-month schedule
 - 4 subjects will receive hepatitis B vaccine comparator:
 - 2 will be vaccinated according to a 0,2,**4**-month schedule
 - 2 will be vaccinated according to a 0,2,**6**-month schedule

Estimated Time to Complete Enrollment: 3 months

Schematic of Study Design:

Group Allocation: Open sequential enrollment

Within Group IP Allocation: Double-blind randomized assignment

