3 STUDY DESIGN

The study will be conducted as a randomized, placebo-controlled, double-blind Phase 1 dose-escalating clinical trial in healthy children between the ages of 6 and 10 years, inclusive, living in the hookworm-endemic area of Lambaréné, Gabon. The study is designed to evaluate the safety, reactogenicity, and immunogenicity of Na-GST-1/Alhydrogel® co-administered with Na-APR-1 (M74)/Alhydrogel®, as compared to the hepatitis B vaccine, in this age group.

Prior to beginning study-related activities, the consent and cooperation of representative community members will be sought, after which parents of potential pediatric participants will be invited to learn about the study and consent to the participation of their child. After a parent or legal representative provides written informed consent for the child's participation and passes the informed consent comprehension questionnaire, the child will undergo eligibility screening, including a complete medical history, physical examination, hematology testing, liver and renal function testing, HIV antibody testing, Hepatitis B and C serology, and urinalysis. In addition, a fecal examination will be performed for ova and parasites, and urine will be examined for *S. haematobium* ova. All clinically significant abnormalities will be reviewed with parents/legal guardians and referral of the child for follow-up care will be provided. After screening, those children determined to be eligible, based on the inclusion and exclusion criteria, will be invited to participate in the study.

Sixty children will be progressively enrolled into 1 of 3 Groups over a projected 3-month enrollment period, with each child followed for 9 months after the final injection (i.e., until Study Day 380 for those receiving vaccinations according to a 0,2,4-month schedule and until Study Day 448 for those receiving vaccinations according to a 0,2,6-month schedule). Group enrollment will be done in an open sequential fashion, whereas within each Group, investigational product (IP) assignment and vaccination will be done in a randomized double-blind fashion.

60 subjects will be enrolled into 3 groups of 20:

The first 20 subjects will be recruited and enrolled into Group 1:

- Group 1 double-blind IP allocation (n=20):
 - 16 subjects will receive 10µg Na-APR-1 (M74) plus 5µg GLA-AF delivered by IM injection in the deltoid muscle, with 10µg Na-GST-1 administered IM in the alternate arm.

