5.1.2 Formulation, Packaging, and Labeling

5.1.2.1 *Na-APR-1 (M74)/Alhydrogel®*

Na-APR-1 (M74)/Alhydrogel® is supplied as a sterile milky-white suspension (when shaken slightly). Each 2.0 ml vial contains a 0.1 mg/ml suspension of *Na-APR-1 (M74)* adsorbed to 0.8 mg/mL of *Alhydrogel®* in a solution containing 10 mM imidazole, 150 mM sodium chloride and 0.3% Empigen BB, with pH 7.4 ± 0.1. The maximum dose that will be administered is 100 µg of *Na-APR-1 (M74)*, or 1.0 ml of the final drug product. This volume contains the equivalent of approximately 400 µg aluminum. Lower doses of *Na-APR-1 (M74)* are delivered by injecting smaller volumes of the 0.1 mg/ml suspension: for example, 0.3 ml will be injected to deliver 30 µg *Na-APR-1 (M74)*. For all doses, the ratio of *Na-APR-1 (M74)* to *Alhydrogel®* will therefore remain constant: for the 30 and 100 µg doses of *Na-APR-1 (M74)* the respective amounts of *Alhydrogel®* will be 240 and 800 µg (corresponding to approximately 120 and 400 µg aluminum, respectively). *Na-APR-1 (M74)* protein expression was completed at Fraunhofer Center for Molecular Biotechnology (FhCMB/Newark, DE) and purification and vialing at the Walter Reed Army Institute of Research (WRAIR/[name]). The product conforms to established requirements of purity, sterility, safety, and identity. In this study, each dose of *Na-APR-1 (M74)/Alhydrogel®* will be administered in combination with 5 µg GLA-AF.

5.1.2.2 *Na-GST-1/Alhydrogel®*

Na-GST-1/Alhydrogel® is supplied as a sterile milky-white suspension (when shaken slightly). Each 2.0 ml vial contains 1.35 ml of a 0.1 mg/ml suspension of *Na-GST-1* adsorbed to 0.8 mg/ml of *Alhydrogel®* in a buffer consisting of 10% glucose and 10 mM imidazole, pH 7.4. Glucose acts as an excipient and imidazole as the buffer based on evidence that these components specifically

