2. Frequency of study vaccine-related serious adverse events from the time of the first study vaccination through approximately 9 months after the last study vaccination.
3. Frequency of clinical safety laboratory adverse events.
4. Frequency of unsolicited adverse events, graded by severity, from the time of each study vaccination through approximately 1 month after each study vaccination.
5. Frequency of new-onset chronic medical conditions through approximately 9 months after the third study vaccination.
6. Frequency of Adverse Events of Special Interest through approximately 9 months after the third study vaccination.

Analysis Plan:

- a. The proportion of participants with at least one injection site AE will be compared by vaccine and dose cohort. We will test the null hypotheses that the type and number of adverse events is the same across all groups by Fisher's exact test.
- b. Laboratory results (hematological and clinical chemistry) will be examined for trends over time and any clinically significant values for individuals will be reported.

Secondary Objective: To determine the doses of co-administered Na-APR-1 (M74) and Na-GST-1 that result in the highest levels of IgG antibody approximately 14 days after the third vaccination.

Secondary Outcome Measure:

The following parameters will be evaluated for each dose of Na-APR-1 (M74) co-administered with Na-GST-1:

1. The IgG level by a qualified indirect ELISA approximately 14 days after the third vaccination.

Analysis Plan:

- a. The proportion of participants with detectable anti-Na-GST-1 and anti-Na-APR-1 (M74) responses will be summarized as a descriptive measure.
- b. IgG levels will be displayed graphically by study group using notched box plots.
- c. Geometric mean antibody responses will be compared between vaccine formulation and dose groups. Comparisons between groups will be made by a one-way analysis of variance (ANOVA) with pair-wise comparisons between groups made by contrasts.
- d. Geometric mean antibody responses for each antigen will be compared using a regression model with main effects for the doses of Na-APR-1 (10, 30 or 100 μ g), and Na-GST-1 (10, 30 or 100 μ g).

Tertiary Objective 1: To assess and compare the duration of antibody responses to Na-GST-1 and Na-APR-1 (M74).

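### The synopsis fixes Na-GST-1 at a single 100 µg dose, but the group allocation gives 10, 30 and 100 µg: a ten-fold conflict for hookworm-vaccine recipients in Group 1

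*Combined protocol and SAP*

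**What the plan says.** The synopsis describes the products under its heading for interventions. Item (a) gives Na-APR-1 at three doses, obtained by varying the injected volume. Item (b) then says that a single dose of Na-GST-1 "will be tested (100µg), at a volume of 1.0ml delivered IM to the deltoid".

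Further on, the synopsis allocates Na-GST-1 by group:

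- Group 1: "with 10 µg *Na-GST-1* administered IM in the alternate arm"
- Group 2: "with 30µg *Na-GST-1* administered IM in the alternate arm"
- Group 3: "with 100 µg *Na-GST-1* administered IM in the alternate arm"

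Other sections follow the three-dose pattern:

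- Section 3 repeats the allocation; for Group 1 it reads "with 10µg Na-GST-1 administered IM in the alternate arm".
- Section 1.2.2 gives a rationale for the three levels of both antigens.
- Section 4.3.3 refers to 10 and 30 µg of both.
- Section 5.1.2.2 treats 100 µg as the maximum and says that lower doses use smaller volumes.
- Section 10.3 specifies a regression with main effects for Na-APR-1 dose "and Na-GST-1 (10, 30 or 100" µg).

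**The concern.** Item (b) sits in the part of the synopsis that defines what is injected, so it cannot be set aside as background. It does not read as an obvious slip either. It follows an item describing several doses, it says in contrast that there is one, and its dose and volume agree with each other.

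Two things are at stake. The first is dosing in children aged 6 to 10. The synopsis states "The first 20 subjects will be assembled and enrolled into Group 1", and Sections 3 and 8.6.2 require written approval from the Safety Monitoring Committee before Groups 2 and 3 but describe no such step before Group 1. The largest discrepancy therefore falls on the first children vaccinated, ahead of any escalation review.

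The second is interpretation. If Na-GST-1 were constant, that antigen would not be escalated in children. The secondary objective, which seeks the doses of both antigens giving the highest IgG, would have no Na-GST-1 doses to compare.

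**Working it through.** **Inputs.**

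- Concentration, from Section 5.1.2.2: "Each 2.0 ml vial contains 1.35 ml of a 0.1 mg/ml suspension of" Na-GST-1, with Alhydrogel at 0.8 mg/ml and about 400 µg aluminum per 1.0 ml.
- Item (b): 100 µg in 1.0 ml.
- Group doses: 10, 30 and 100 µg (synopsis and Section 3).
- Each group: 16 hookworm-vaccine recipients and 4 hepatitis B controls, with three vaccinations per child.

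**Item (b) on its own terms.** Dose = concentration × volume: 0.1 mg/ml × 1.0 ml = 0.1 mg = 100 µg. Its dose and volume agree. The vial fill of 1.35 ml covers every volume from 0.1 to 1.0 ml, so packaging does not separate the readings.

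**Item (b) against the allocation.** Volume = dose / (100 µg/ml). Alhydrogel = 800 µg/ml × volume. Aluminum ≈ 400 µg/ml × volume. Ratio = 100 / allocated dose.

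| Group | Allocated dose | Volume | Alhydrogel | Aluminum (approx.) | Item (b) dose | Ratio |
|---|---|---|---|---|---|---|
| 1 | 10 µg | 0.1 ml | 80 µg | 40 µg | 100 µg | 10.0 |
| 2 | 30 µg | 0.3 ml | 240 µg | 120 µg | 100 µg | 3.33 |
| 3 | 100 µg | 1.0 ml | 800 µg | 400 µg | 100 µg | 1.0 |

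Section 5.1.2.2 states the Alhydrogel and aluminum amounts for 30 and 100 µg. The Group 1 entries are derived at the same ratio. The document gives no Na-GST-1 volume for 10 µg.

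**Children and injections affected.** Groups 1 and 2: 16 × 2 = 32 of 16 × 3 = 48 hookworm-vaccine recipients. Injections: 32 × 3 = 96 of 48 × 3 = 144.

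**Does any other section settle it?** Section 5.2 says only that suitable volumes are drawn up. Section 4.3.3 pairs 10 µg with Groups 1 and 2 and 30 µg with Groups 3 and 4, which does not fit a three-group trial. The primary objective and the staggering rationale in Section 3 speak of varying Na-APR-1 only, which is compatible with either reading.

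**Effect on the Section 10.3 regression.** Code the model as an intercept, two indicators for Na-APR-1 dose and two for Na-GST-1 dose: 5 columns. Over the 48 vaccine recipients the design matrix has rank 3 under both readings, but the estimable quantity differs:

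- Under the group allocation, the two doses rise together. The joint dose effect can be estimated; the separate effects cannot.
- Under item (b), the Na-GST-1 columns are constant. Only a Na-APR-1 dose effect can be estimated.

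A difference between groups in anti-Na-GST-1 IgG would thus reflect a joint dose response in one case. In the other it would reflect the influence of Na-APR-1 dose on the response to a constant Na-GST-1 dose.

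**The case against.** The strongest reply is that one sentence stands against many. The synopsis group lists, the dose rationale, Section 3, the product description and the analysis plan all carry three Na-GST-1 doses. A careful reader could infer the intention, and nothing shows that syringes are filled from the synopsis. In addition, 100 µg is not above the maximum already given to adults (Section 1.2.2).

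The imbalance is real and lowers the chance that anyone is misled. It does not remove the defect: the preparation section gives no Na-GST-1 volumes, so the dose is left to inference in a pediatric escalation trial.

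Two limits stand. The conflict does not touch the 4 hepatitis B controls in each group. Reconciling the texts would also not rescue the regression with separate main effects, because under the allocation the two antigen doses are fully confounded. What depends on this conflict is whether any Na-GST-1 dose contrast exists at all.

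**Conclusion.** The concern holds. The document gives two incompatible statements of the Na-GST-1 dose, both within the synopsis, and never reconciles them. The disagreement is 10-fold for the 16 hookworm-vaccine recipients in Group 1, 3.33-fold for the 16 in Group 2 and nil in Group 3. The size rests only on the stated concentration, the stated group doses and three planned vaccinations per child; the Group 1 volume and aluminum figures also assume the constant ratio in Section 5.1.2.2. The loss of the Na-GST-1 dose comparison is conditional: it follows if item (b) is the reading applied. Because the conflict concerns what is injected into the first children enrolled, it should be resolved before vaccination starts. This conclusion does not depend on which statement was intended.

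**What to change.** The sponsor should confirm the intended Na-GST-1 dose for each group and reconcile synopsis item (b), the synopsis group lists and Sections 1.2.2, 3, 4.3.3, 5.1.2.2, 5.2 and 10.3 with it. A short table of group, Na-GST-1 dose and injected volume, placed in Section 5.2 and cited elsewhere, would leave one source for the figures and supply the Group 1 volume if that group's dose is 10 µg. The group numbering in Section 4.3.3 should be corrected at the same time.

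The cost depends on the answer. If the group allocation is confirmed, the dose conflict is removed by amending item (b); the table and the numbering are further small edits. If the single dose is confirmed, the allocation lists, the dose rationale, the secondary objective and the regression all need revision. Either way, no change in sample size follows from the reconciliation itself.

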1 BACKGROUND INFORMATION AND SCIENTIFIC RATIONALE

1.1 Background Information

1.1.1 Hookworm Infection and Justification for Vaccine Development

There is an urgent need for new tools to control human hookworm infection and to reduce its burden of disease in developing countries. This is especially important for children and women of reproductive age who represent populations that are highly vulnerable to the effects of hookworm disease. Up to 65,000 deaths annually have been attributed to human hookworm infection (1). However, the mortality figures pale in comparison to global disease burden estimates that suggest that hookworm may account for the loss of up to 22 million Disability Adjusted Life Years annually (2), mainly due to the direct and indirect effects of acute and chronic anemia.

Human hookworm infection is a soil-transmitted helminth infection caused by the nematode parasites *Necator americanus* and *Ancylostoma duodenale*. It is one of the most common chronic infections of humans, affecting over 400 million people in the developing nations of the tropics (2). The largest number of cases occurs in impoverished rural areas of sub-Saharan Africa, Southeast Asia, China, and the tropical regions of the Americas. Approximately 3.2 billion people are at risk for hookworm infection in these areas. *N. americanus* is the most common hookworm worldwide, whereas *A. duodenale* is more geographically restricted (3).

Hookworm transmission occurs when skin comes into contact with infective third-stage larvae (L3) in fecally contaminated soil. The L3 have the ability to penetrate the skin, usually of the hands, feet, arms, buttocks and legs. The L3 invade human tissues and enter the gastrointestinal tract where they molt to the adult stage approximately 5-9 weeks following initial host entry. Adult hookworms are approximately 1 cm long parasites that cause host injury by attaching to the mucosa and submucosa of the small intestine to produce intestinal blood loss. There is a direct relationship between hookworm intensity (as determined by fecal egg counts) and host blood loss; typically the presence of between 40 and 160 adult hookworms in the intestine results in blood loss sufficient to cause anemia and malnutrition. The term “hookworm disease” refers primarily to the iron deficiency anemia and protein losses that occur in moderate and heavy infections (4). When host iron stores become depleted, there is a direct correlation between hookworm intensity and reduced host hemoglobin, serum ferritin, and protoporphyrin. Because of their low iron stores, children and women of reproductive age are the populations considered the most vulnerable to hookworm-associated blood loss (4-11).

In children, chronic hookworm infection and the resultant iron deficiency anemia have been shown to impair physical and intellectual development (3, 12, 13). Preschool children are particularly vulnerable to the effects of hookworm anemia and disease (8). In addition to its health impact on children, hookworm infection also affects adults. Unlike other soil-transmitted helminth infections such as ascariasis and trichuriasis, in which the highest intensity infections occur almost exclusively in school-aged children, it has been shown that high-intensity hookworm infections may also occur in adults (14-16).

The primary approach to hookworm control worldwide has been the frequent and periodic mass administration of benzimidazole anthelmintics to school-aged children living in high-prevalence areas. In 2001, the World Health Assembly adopted Resolution 54.19, which urges member states to provide regular anthelmintic treatment to high-risk groups with the target of regular treatment of at least 75% of all at-risk school-aged children. However, cure rates for a single dose of a benzimidazole are sub-optimal, particularly for mebendazole (17-20). These concerns have prompted interest in developing alternative tools for hookworm control (3, 21, 22). Vaccination to prevent the anemia associated with moderate and heavy intensity hookworm infection would alleviate the public health deficiencies of drug treatment alone.

The feasibility of developing a hookworm vaccine is based on the previous success of using live, irradiated hookworm larvae (L3 stage) as a vaccine for canine hookworm infection. This provided the experimental basis for the commercial development of a canine hookworm vaccine, which was marketed in the United States during the early 1970s. However, it is not realistic to develop a live L3 vaccine for humans due to multiple reasons including high production costs, challenging storage requirements, a short shelf life, and a lack of sterilizing immunity.

Alternatively, the strategy being pursued is to identify key hookworm proteins to which protective immune responses are directed in the animal models for this infection (namely the canine model) and to produce these as recombinant proteins that could then be used as vaccine antigens. This effort focused initially on identifying antigens expressed by the invading larvae (L3). In addition, a separate strategy has been to identify targets of the adult stage of the hookworm lifecycle; since hookworms attach onto the intestinal lumen and ingest host blood, antibodies could also be ingested that if directed against key hookworm proteins, would interfere with their function, ultimately resulting in the death or reduced fecundity of the worm.

